The descriptive statistical analysis was carried out in the following way: for the qualitative variables proportions and percentage rates (%) were reported; for the quantitative variables, mean and standard deviation or median and interquartile range (Q1 to Q3) were reported according to the distribution of the data. The normality of the distribution was determined by the Kolmogorov-Smirnov test.

The univariate inferential analysis was performed using the chi-square test or Fisher's exact test for the qualitative variables, according to the distribution of the expected values in the contingency table. For the numerical variables, the t test was used for two independent samples or its non-parametric version, according to the nature of the distribution of the numerical data. A p value <0.05 was considered significant.

For the analysis of the treatment, the risk analysis model will be used with the calculation of the RR, RAR, RRR, its 95% Confidence Interval (95% CI) and the NNT was determined for the traditional scheme, once the data were concluded. The analysis was considered by protocol and by intention to treat.

RESULTS

PATIENTS OF THE STUDY

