A total of 111 hospitalized DM2 patients not critical to the study were evaluated. Of these, 35 did not meet the inclusion criteria and the 76 included participants were randomized into two groups. The recruitment of patients began on November 15, 2017 and ended on June 1, 2018. The "physiological" insulin group with 37 participants and the traditional group with 39 participants. Within the "physiological" group, 1 patient was eliminated before initiating the insulin regimen, presenting acute abdomen and requiring intensive therapy. Therefore, 36 patients in the "physiological" group and 39 patients in the traditional group began treatment, who entered the analysis for intention to treat. From the physiological group 6 patients did not conclude the treatment by discharge before the control and 2 patients due to poor adherence to the treatment. In the traditional group, 5 patients withdrew before the control, 1 patient due to poor adherence to treatment, 1 patient died before the control, and 1 patient was suspended due to critical condition. At the end of the study, 28 patients in the "physiological" group and 31 patients in the traditional group were completed in the analysis per protocol. In 20 (71.4%) patients in the first group and in 30 (96.8%) patients in the second group, treatment was completed until discharge.

POPULATION CHARACTERISTICS

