The number of days to reach control during the hospital stay statistically were not different between groups (by protocol 4.9 ± 2.2 days vs 4.7 ± 2.4 days, $p = 0.553$, by intention to treat 4.9 ± 2.1 days vs 4.7 ± 2.3 days, $p = 0.445$).

SAFETY RESULTS

Safety was evaluated with episodes of hypoglycemia and complications associated with diabetes. In the "physiological" group it was observed that 15 (41.6%) patients had at least one event of hypoglycemia during their entire stay; On the other hand, in the traditional group 15 (38.4%) presented at least one event of hypoglycemia (per protocol, RR: 1.11, 95% CI: 0.62 to 1.97, $p = 0.729$; intention to treat, RR = 1.08, 95% CI: 0.62 to 1.89, $p = 0.777$). The presence of more than 2 hypoglycemic events during their hospitalization was observed in 8 (22.2%) patients of the "physiological" group and in 2 (5.1%) patients of the traditional group (per protocol, RR = 7.75, 95% CI: 1.02 a 59.13, $p = 0.021$; by intention to treat, RR: 4.33, 95% CI: 0.98 to 19.07, $p = 0.041$).

In the analysis by protocol, the rate of the number of total events / patients with hypoglycemia in the "physiological" group was 2.4 ± 1.3 events / patient, while in the traditional group it was 1.6 ± 0.7 events / patient ($p = 0.129$) ; in the intention-to-treat analysis in the "physiological" group it was 2.5 ± 1.6 events / patient, whereas in the traditional group it was 1.7 ± 0.9 events / patient ($p = 0.182$).

Thirty-eight hypoglycemic events were found in the "physiological" group and 26 hypoglycemic events in the traditional group; of which, 36 were mild hypoglycemia in the "physiological" group and 24 events in the traditional group (RR per protocol: 1.02, 95% CI: 0.91 to 1.19, $p = 1.0$; RR by intention to treat: 1.03, 95% CI: 0.90 to 1.17, $p = 1.0$).

Regarding the complications associated with diabetes, soft tissue infection was the most frequent, one patient had pneumonia, one acute renal failure, one acute

respiratory failure, and no patient presented bacteremia, diabetic ketoacidosis or hyperosmolar state. Two of the patients included in the study died from complications not associated with hypoglycemia, one in the physiological group secondary to progression of the infectious process, sepsis and septic shock, and one in the group Traditionally associated with acute respiratory failure.

SECONDARY RESULTS

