There was a significant difference in the sustained control of blood glucose that was reported in 20 (55.6%) of the cases in the physiological group compared to 30 (76.9%) of the traditional group (per protocol, RR: 0.74, 95% CI: 0.58 to 0.94, $p = 0.009$; by intention to treat, RR: 0.72, 95% CI: 0.51 to 1.01, $p = 0.049$).

The causes of failure of the sustained control were discharge before control in goals, progress to critical state, death before glycemic control, poor adherence to the protocol and suspension for sustained hypoglycemia. With the "physiological" scheme it was necessary to suspend or change by another scheme in 8 (22.2%) patients, in comparison with the traditional scheme where only the scheme was suspended or changed in 1 (2.6%) patient (by intention to treat, RR: 8.67, 95% CI: 1.14 to 65.92, $p = 0.011$). There were no adverse effects to the use of insulin in both groups.

OTHER RESULTS

If the suspension of the scheme is considered for sustained hypoglycemia of 8 patients in the physiological group vs 1 patient in the control group, a risk ratio of 8.67 (95% CI: 1.14 to 65.9) and a number necessary to harm of 5.09 was calculated (95% CI: 2.93 to 19.23) patients with the physiological scheme to produce 1 event of hypoglycemia.

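### Days to reach control is reported as an intention-to-treat mean with no number analysed, although at least 12 of the 75 intention-to-treat patients left or died before control and have no such day

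*Combined protocol and SAP*

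**What the plan says.** The Effectiveness results report that "The number of days to reach control during the hospital stay statistically were not different between groups". Per protocol the figures are 4.9 ± 2.2 against 4.7 ± 2.4 days (p = 0.553). By ITT they are 4.9 ± 2.1 against 4.7 ± 2.3 days (p = 0.445). The physiological arm comes first in each pair. No number analysed stands beside either line.

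The section on patients of the study puts 36 physiological and 39 traditional patients in the ITT set, and 28 and 31 in the per-protocol set. It explains the losses as follows:

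- Physiological arm: "From the physiological group 6 patients did not conclude the treatment by discharge before the control", plus 2 for poor adherence.
- Traditional arm: "In the traditional group, 5 patients withdrew before the control, 1 patient due to poor adherence to treatment, 1 patient died before the control", plus 1 stopped because of critical condition.

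For the analysis of such an outcome the Statistical analysis section says only: "For the numerical variables, the t test was used for two independent samples or its non-parametric version". The document mentions no censoring, competing events or assigned values for this outcome, and does not define control for it.

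**The concern.** A patient who leaves hospital or dies before reaching control has no day of control. A mean of days labelled ITT must then have been obtained in one of two ways:

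- **These patients were left out.** The mean is conditional on an outcome that occurs after randomisation, and the set analysed is no longer the ITT set.
- **They were given a value**, such as the day of exit. The mean then depends on a rule that the document does not state.

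In neither case does the figure estimate time to control among all 36 and 39 patients. The finding of no difference is nevertheless presented as holding by ITT as well as per protocol, so a reader would take it as confirmed in the full set. The per-protocol line is not challenged on this count, because that set excludes the 12 patients by construction.

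**Working it through.** **Inputs.** ITT 36 and 39; per protocol 28 and 31; exits 6 + 2 and 5 + 1 + 1 + 1 (patients of the study). Means, SDs and p-values are from the Effectiveness results.

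**1. Reproduce the patient flow.** 36 − (6 + 2) = 28 and 39 − (5 + 1 + 1 + 1) = 31. Both agree with the stated per-protocol numbers.

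**2. Patients stated to have left or died before control** (Wilson 95% CI).

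| | Physiological | Traditional | Total |
|---|---|---|---|
| Without a day of control | 6/36 = 16.7% (7.9 to 31.9) | 5 + 1 = 6/39 = 15.4% (7.2 to 29.7) | 12/75 = 16.0% (9.4 to 25.9) |
| Observed day of control, at most | 36 − 6 = 30 (83.3%; 68.1 to 92.1) | 39 − 6 = 33 (84.6%; 70.3 to 92.8) | 63/75 = 84.0% |

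Twelve is a minimum, because control status is not stated for the other 4 exits (3 poor adherence, 1 critical condition). If none of those 4 reached control and every per-protocol patient did (implied but not stated), the observed times number 28 and 31, or 59 of 75.

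**3. Do the printed summaries show which patients were used?** The SDs change from per protocol to ITT (2.2 to 2.1; 2.4 to 2.3), so if the ITT calculation contains the per-protocol patients, at least one was added per arm. Eight per arm are available, but at most 8 − 6 = 2 per arm can have an observed day.

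- *Only observed days used (n = 30 and 33).* Adding two patients at the mean gives SD √(27 × 2.2² / 29) = 2.12 and √(30 × 2.4² / 32) = 2.32, which round to the printed 2.1 and 2.3.
- *All 36 and 39 used.* The mean of the 8 added patients is (36 × 4.9 − 28 × 4.9)/8 = 4.9 days (4.5 to 5.3 within rounding) and (39 × 4.7 − 31 × 4.7)/8 = 4.7 days (4.3 to 5.1). Their variance is (35 × 2.1² − 27 × 2.2²)/7 = 3.38 and (38 × 2.3² − 30 × 2.4²)/7 = 4.03. Both are possible values, but at least 6 of the 8 in each arm would carry an assigned time.

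The printed figures fit either reading.

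**4. Do the p-values show it?** A two-sample t test on the ITT summaries gives p = 0.70 with 36/39 (0.55 to 0.85 within rounding) and 0.72 with 30/33 (0.58 to 0.86). The stated value is 0.445. Per protocol with 28/31 it gives 0.74 (0.61 to 0.87); the stated value is 0.553. The stated values do not come from a t test on these summaries. The planned non-parametric test could give them, and that cannot be checked without patient data. The p-values therefore do not identify n and are not shown to be wrong.

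**The case against.** Four points can be made on the other side.

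- **The documented loss is balanced.** The shares are 16.7% and 15.4%, a difference of 1.3 points. This stands, and it is why no direction of bias is claimed. It does not turn a conditional mean into an ITT comparison, because the timing of exits and the prognosis of those who left may still differ.
- **Sustained control already covers the full set.** The Secondary results count early exits as failures on 36 and 39 patients: "The causes of failure of the sustained control were discharge before control in goals, progress to critical state, death before glycemic control". This also supports reading control in the patient flow as glycemic control. But it is a different endpoint and carries no time.
- **The result is a supporting one.** The sample size rests on hypoglycemia, and no consequence for the conclusion is shown. This stands and limits the weight of the point.
- **Stating n, the definition and the rule might be enough.** That would remove the misleading label, but would still leave no estimate of time to control in all patients.

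A stronger reading is tempting. Sustained control was 20/36 against 30/39. In the physiological arm "it was necessary to suspend or change by another scheme in 8 (22.2%) patients", against 1 in the traditional arm. A reader might infer that far fewer physiological patients ever reached control and that the statement of no difference hides this. The documents do not support that. Suspension for sustained hypoglycemia is listed as a cause of failing sustained control, separately from exit before control, and a suspended patient may have reached control first.

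**Conclusion.** The point holds. At least 12 of 75 ITT patients (16.0%; 6/36 and 6/39) have no day of control, so at most 30 and 33 observed times can stand behind means labelled ITT. The document gives neither the number used nor a rule for the rest, and its planned tests make no provision for them. The statement of no difference should not be read as an ITT comparison of time to control.

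This rests on reading control in the patient flow as the same glycemic control that is timed in the Effectiveness results. The wording of the Secondary results supports this, but no definition confirms it.

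A reader might also infer that the comparison is biased towards one arm, or that p = 0.445 is an error. Neither is shown: documented loss is similar in the two arms, and the planned rank-based test cannot be checked from summaries. The other results of the trial are not touched by this point.

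**What to change.** 1. State the definition of control used for this outcome and the number analysed per arm. If times were assigned to patients without control, state the rule.
2. Report the number and proportion reaching control among all 36 and all 39 patients, with 95% CI.
3. Replace the ITT mean with the cumulative incidence of first control in all 36 and 39, treating exit, critical state or death before control as competing events.
4. Keep a mean of days only if it is given with its n and labelled as describing patients who reached control.

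A Kaplan-Meier and log-rank analysis censored at exit is optional, as a sensitivity analysis, with the caveat that censoring at discharge or death may be informative.

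**Cost.** One analysis is replaced and two statements are added. It needs the day of first control and the day and reason of exit for each patient. The section on patient monitoring says that glucose was measured several times a day and recorded on the nursing sheet; that these days can be tabulated from those records is an assumption. The downside is a little more work and a less precise result. If the days cannot be recovered, items 1 and 4 alone would still remove the misleading label.

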Of the total patients analyzed for intention to treat, 34 (45.3%) patients were men and 41 (54.7%) women. According to the place of hospitalization, 18 (24%) were in the internal medicine service, 29 (38.7%) in traumatology and orthopedics and 28 (37.3%) in general surgery. The mean age of the patients was 57.83 ± 13 years. The average body mass index was 26 ± 5.1 kg / m². The mean random glucose at admission was 230.5 ± 70.2 mg / dL, the glycosylated hemoglobin level was $8.3 \pm 2.3\%$, and the serum creatinine was 1 ± 0.5 mg / dL. The treatment before admission was with oral hypoglycemic agents in 25 (33.3%) patients, with insulin in 25 (33.3%) patients, the combination of oral hypoglycemic agents and insulin in 12 (16%) patients and 13 (17.3%) patients. they received treatment or were diagnosed at the time of admission. The average dose of insulin administered was 29.6 ± 11.6 IU and the number of days of hospital stay was 9.3 ± 5 days. The reasons for admission to the hospital were: abscesses and soft tissue infection, hip fracture, diabetic foot, other fractures, cancer, heart disease, gastrointestinal bleeding, acute cholecystitis, stage IV chronic kidney disease, pneumonia, gonarthrosis, pathway infection urinary tract, intoxications, meningitis, alveolar obesity-hypoventilation syndrome, peripheral thrombosis and obstructive uropathy.

EFFECTIVENESS RESULTS

When evaluating efficacy, by protocol, the following was observed: The fasting glucose average in the "physiological" group was 130.3 ± 20.9 mg / dl, while in the traditional group it was 126 ± 22 mg / dl ($p = 0.114$); the average postprandial glucose in the physiological group was 150.8 ± 22.8 mg / dl and in the traditional group it was 149.4 ± 28.1 mg / dl ($p = 0.833$). The average morning glucose in the first group was 130.9 ± 18.3 mg / dl and 125.9 ± 26.7 mg / dl in the second group ($p = 0.081$).

In the analysis by intent to treat in the same way control was achieved in goals in both groups. The average fasting glucose in the "physiological" group was 135 ± 22.6 mg / dl, while in the traditional group it was 129.6 ± 23.6 mg / dl ($p = 0.114$); the average postprandial glucose in the physiological group was 156.2 ± 27.2 mg / dl and in the traditional group it was 155.4 ± 29 mg / dl ($p = 0.902$). The average morning glucose in the first group was 136.2 ± 21.2 mg / dl and 127.4 ± 26.6 mg / dl in the second group ($p = 0.081$).

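### The only hypoglycemia rate divides events by patients who had hypoglycemia, so it compares groups selected on the outcome and ignores time at risk

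*Combined protocol and SAP*

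**What the plan says.** All references are to the combined protocol and SAP.

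- **STATISTICAL ANALYSIS** plans risk ratios and related measures, by protocol and by intention to treat. It sets no window for counting events, no rule for events after a scheme is suspended, and no exposure denominator.
- **SAFETY RESULTS** uses the whole stay: "15 (41.6%) patients had at least one event of hypoglycemia during their entire stay", and "in the traditional group 15 (38.4%) presented at least one event of hypoglycemia". The risk ratios are 1.08 (0.62 to 1.89) by intention to treat and 1.11 (0.62 to 1.97) per protocol.
- The same section gives 38 and 26 events in total. Its rate is events over patients with hypoglycemia: 2.5 ± 1.6 vs 1.7 ± 0.9 by intention to treat (p = 0.182) and 2.4 ± 1.3 vs 1.6 ± 0.7 per protocol (p = 0.129).
- **POPULATION CHARACTERISTICS** gives exposure only for both arms together: the "number of days of hospital stay was 9.3 ± 5 days". Days on scheme are not reported.
- **PATIENTS OF THE STUDY**, on the per-protocol sets of 28 and 31: "In 20 (71.4%) patients in the first group and in 30 (96.8%) patients in the second group, treatment was completed until discharge".
- **SECONDARY RESULTS**: in the physiological arm "it was necessary to suspend or change by another scheme in 8 (22.2%) patients", while in the traditional arm "only the scheme was suspended or changed in 1 (2.6%) patient". **OTHER RESULTS** attributes these 8 and 1 suspensions to sustained hypoglycemia.

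**The concern.** Dividing by affected patients drops everyone without an event. The two groups left are defined by something that happened after randomization, so the comparison no longer has the protection of randomization. It also answers a narrower question (how many events, given at least one) than the one a clinician would ask (how many events per patient, or per day, under each scheme).

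Time matters because a longer stay gives more chances to record an event, and stays here have an SD of 5 days on a mean of 9.3. Within the per-protocol set, an unequal number of patients (8 vs 1) also stopped receiving the assigned scheme before discharge. A whole-stay event total may therefore mix time on and off the scheme to different degrees in the two arms.

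The trial was sized on a difference in hypoglycemia. A reader sees a near-neutral any-event ratio and a non-significant rate, next to marked differences in recurrent events and in suspensions. No figure puts all events over all treated patients and their time at risk.

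**Working it through.** **1. The printed risk ratios reproduce.** Ratio of proportions, 95% CI on the log scale with SE = √(1/a − 1/n + 1/b − 1/m).
- Intention to treat, 15/36 vs 15/39: 1.083 (0.622 to 1.885), p = 0.777, as printed.
- Per protocol, counts are not printed. Among equal counts in the two arms, which all give a ratio of 1.107, only 13/28 vs 13/31 matches the printed interval: 1.107 (0.623 to 1.966).

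**2. The denominator of the rate.** 38/15 = 2.53 and 26/15 = 1.73 match the printed 2.5 and 1.7. The denominator is therefore the 15 affected patients in each arm, not the 36 and 39 treated and not days.

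**3. The same events over all treated patients.**
- 38/36 = 1.06 and 26/39 = 0.67; ratio 1.583.
- Naive Poisson SE of the log ratio = √(1/38 + 1/26) = 0.2545; 95% CI 0.96 to 2.61.
- The ratio factors as 1.083 (any event) × 38/26 = 1.462 (events per affected patient). The report shows these two pieces separately and never their product.

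**4. Rough allowance for clustering.** From the printed SDs, with zeros added for unaffected patients:
- Physiological: sum of squares 14 × 1.6² + 38²/15 = 132.1; variance over 36 patients (132.1 − 38²/36)/35 = 2.63, which is 2.5 times the mean.
- Traditional: 14 × 0.9² + 26²/15 = 56.4; variance over 39 patients (56.4 − 26²/39)/38 = 1.03, which is 1.5 times the mean.
- Robust SE = √(2.63/(36 × 1.056²) + 1.03/(39 × 0.667²)) = 0.353; 95% CI about 0.79 to 3.16.

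**5. Time at risk.** Assume a mean stay of 9.3 days in both arms. Patient-days are 36 × 9.3 = 334.8 and 39 × 9.3 = 362.7, so the rates are 11.35 and 7.17 per 100 patient-days, again a ratio of 1.58. If mean stays differed by 2 days (10.3 vs 8.3, hypothetical), the ratio would be 1.583 × 8.3/10.3 = 1.28, or 1.583 × 10.3/8.3 = 1.96 the other way round. The documents do not allow a choice within that range.

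**6. Where the suspended patients sit.** Per protocol, 28 − 20 = 8 and 31 − 30 = 1 did not stay on scheme to discharge, the same 8 and 1 that SECONDARY RESULTS gives. By intention to treat, 36 − 20 = 16 = 8 outside the per-protocol set + 8 suspended, and 39 − 30 = 9 = 8 + 1. The suspended patients are therefore inside the per-protocol set: 28.6% vs 3.2%. (A further traditional patient, stopped for critical condition, is among the 8 outside it.)

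**7. What dropping off-scheme days would do.** Suspension was for sustained hypoglycemia, so each of the 8 and 1 already had an event before it. Any-event counts would be expected to stay at 15/36 vs 15/39 and 13/28 vs 13/31. Event totals could fall and days would fall. If all events are kept and L days are removed for each suspended patient, the ratio becomes 1.65 for L = 2, 1.73 for L = 4 and 1.86 for L = 7. That rise comes from deleting days alone.

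**The case against.** The strongest defense is that the trial was sized and planned on proportions. Any event over the stay, by assigned arm, is a standard intention-to-treat measure. That stands, and this point leaves that result alone. It is also true that nothing printed suggests unequal stays, that time to glycemic control was similar (4.9 vs 4.7 days), and that the affected rates were non-significant as printed.

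A reader might infer more than the documents support, in three ways.

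- *That the any-event ratios are distorted by days off the scheme.* They are not expected to be, for the reason in step 7.
- *That an identifiable number of events occurred off scheme*, for example those after a patient's third event. The printed totals, means, SDs and counts with more than 2 events, taken with per-protocol patients as a subset of all treated, imply 6 such events in the physiological arm. Three of these belong to one patient outside the per-protocol set, who is not among the suspended. Only 7 per-protocol physiological patients had more than 2 events (7/28 vs 1/31 gives the printed 7.75), yet 8 were suspended, so a third event does not mark suspension. The suspension rule also excepts fasting and allows restart. No event timing is given.
- *That the per-protocol analysis should simply be redefined on assigned-scheme days.* Follow-up would then stop because of the outcome, in 8 vs 1 patients, which brings in a bias of its own.

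What remains is the denominator: the one reported rate is conditioned on the outcome, and exposure by arm is not given.

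**Conclusion.** The point holds for the event rate and the missing exposure, not for the any-event results. Over all treated patients the physiological arm had 1.06 events per patient against 0.67, a ratio of 1.58. The naive interval is 0.96 to 2.61, and a rough allowance for clustering from the printed SDs gives about 0.79 to 3.16. Neither interval excludes 1, so this does not show a higher rate in the physiological arm. It shows that the reported rate does not answer the question and that the data leave a wide range open.

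Reading 1.58 as a per-day ratio assumes equal mean stay in the two arms, which the documents neither confirm nor contradict. The event totals and events per patient could change if days after suspension were set aside. By how much, or whether at all, cannot be told without event dates.

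**What to change.** 1. Keep the whole-stay any-event result as the intention-to-treat comparison.
2. Replace events per affected patient with events per patient-day over all treated patients, from a negative binomial model or a Poisson model with robust standard errors, with log days as offset.
3. Report length of stay and days on the assigned scheme by arm.
4. Add an analysis limited to assigned-scheme days as a sensitivity analysis only. State beside it that follow-up ends because of hypoglycemia in 8 vs 1 patients, so the censoring is informative.

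The cost is a reanalysis of readings already on the nursing sheets, assuming that dates of events, suspension and discharge can be recovered. Intervals will be wider than the naive Poisson ones once overdispersion is allowed for. No new data collection is needed.

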B. Insulin adjustment:

- If fasting capillary glucose is <140 mg/dl in the absence of hypoglycemia: no change.

- If fasting capillary glucose is between 140 and 180 mg/dl: the total insulin dose increases by 10%.

- If fasting capillary glucose is >180 mg/dl: increase the total insulin dose by 20%.

- If fasting capillary glucose is <70mg/dl, decrease the daily dose of total insulin by 20%.

C. Supplemental Insulin: Administer supplemental insulin lispro in addition to NPH insulin programmed for baseline glucose greater than 180 mg/dL using a supplemental insulin protocol (Annex 1). If fasting or postprandial capillary glucose persists >180mg/day despite the previously assigned scheme:

- If a patient can eat all or most of their meals, administer supplemental insulin Lispro following the "usual" column.

- If a patient cannot eat, is >70 years old, soft tissue infection or has a glomerular filtration rate of 16-30ml/min, administer supplemental insulin Lispro following the "insulin-sensitive" column.

- If the capillary glucose is persistently >180 mg/dl in the absence of hypoglycemia, increase the insulin scale from the "sensitive" to "usual" column or from the "usual" column to the "resistant" column.

3. Management of Hypoglycemia

If a capillary glucose measurement of the patient has <70mg/dl, either by hourly capillary glucose or by the presence of clinical symptoms (sweating, chills, dizziness, nausea, hunger, blurred vision, numbness, paresthesia of the lips or tongue) and is alert, provide oral feeding equivalent to 15 grams of carbohydrates (1 serving of food or 1-2 tablespoons of sugar) or 30ml of 50% glucose solution.

If the patient presents altered state of consciousness (drowsiness, confusion, or stupor) or does not tolerate the oral route, apply 30ml of 50% glucose solution (15 grams of carbohydrates) and 15 minutes later take a new capillary blood glucose measurement. If glucose levels continue <70mg / dl, a new dose of 15g of

carbohydrate is applied every 15 minutes until glucose >70mg/dl is reached.

If during the study patients present more than 1 event of hypoglycemia after adjustment with a 20% decrease in insulin dose after a first event, in the absence of fasting, suspend the insulin regimen. Only restart insulin scheme in the case of disappearance of the hypoglycemia risk factor.

STATISTICAL ANALYSIS

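### In the Safety Results, the only hypoglycemia event comparison with p<0.05 uses a cut (more than 2 events) that the statistical section does not name; at the adjacent cut the risk ratio falls from 4.33 to about 1.22

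*Combined protocol and SAP*

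**What the plan says.** The Statistical Analysis section sets out the treatment comparison in general terms: "For the analysis of the treatment, the risk analysis model will be used with the calculation of the RR, RAR, RRR", with confidence intervals and a number needed to treat. It adds chi-square or Fisher tests for categorical variables and a p<0.05 rule. It gives no threshold for repeated hypoglycemia. The Sample Size paragraph is based on a 25% difference in the hypoglycemia rate, also without a count threshold.

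The Safety Results then report four kinds of hypoglycemia event comparison:
- At least one event: 15 v 15 patients, ITT RR 1.08, p = 0.777.
- More than 2 events: "The presence of more than 2 hypoglycemic events during their hospitalization was observed in 8 (22.2%) patients" in the physiological group and "in 2 (5.1%) patients of the traditional group". ITT RR 4.33 (0.98 to 19.07), p = 0.041; per protocol RR 7.75 (1.02 to 59.13), p = 0.021.
- Events per affected patient: ITT 2.5 ± 1.6 in the physiological group, "whereas in the traditional group it was 1.7 ± 0.9 events / patient" (p = 0.182); per protocol 2.4 ± 1.3 v 1.6 ± 0.7 (p = 0.129).
- Totals: "Thirty-eight hypoglycemic events were found" in the physiological group and 26 in the traditional group, with the mild share compared at p = 1.0.

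The number of patients with at least 2 events is not given.

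**The concern.** Only the second comparison meets the plan's p<0.05 rule, and its threshold does not appear in the statistical section. The adjacent threshold, at least 2 events, is skipped. When a count is split at one chosen point, the estimate can depend on where the split falls, so the neighbouring splits need to be seen.

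A reader of the Safety Results would take away a four- to eight-fold excess of repeated hypoglycemia on the physiological scheme. Hypoglycemia is the quantity on which the trial was sized, so it matters whether that size of effect survives a change of cut.

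**Working it through.** **Inputs.** Denominators are 36 and 39 (ITT) and 28 and 31 (per protocol), from Patients of the Study. Everything else is from the Safety Results. RR = (a/n₁)/(b/n₂); SE of ln RR = √(1/a − 1/n₁ + 1/b − 1/n₂); CI = exp(ln RR ± 1.96 SE).

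**1. Reproduce the printed result.** For 8/36 v 2/39, RR = 0.2222/0.0513 = 4.33. SE = √(0.1250 − 0.0278 + 0.5000 − 0.0256) = 0.756, giving a CI of 0.985 to 19.07. Fisher p = 0.0418, matching the printed 0.041 if truncated. Chi-square gives 0.030, and 0.066 with Yates correction. Per protocol, the printed RRs and CIs are returned by 13/28 v 13/31 (at least one event: 1.11, 0.62 to 1.97) and 7/28 v 1/31 (more than 2: 7.75, 1.02 to 59.13).

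**2. Traditional arm, ITT.** There are 15 affected patients, 26 events, two patients above 2, and SD 0.9. Let those two have a and b events, k patients have 2, and 13 − k have 1. The total requires k = 13 − a − b, so the sum of squares is S = 52 + a(a − 3) + b(b − 3). An SD that rounds to 0.9 needs S = 26²/15 + 14·SD² between 55.2 and 57.7.
- (3,3): S = 52, SD 0.70
- (4,3): S = 56, SD 0.88
- (4,4): S = 60, SD 1.03
- (5,3): S = 62, SD 1.10, and S only rises from there

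Only (4,3) fits, so k = 6: one patient with 4 events, one with 3, six with 2 and seven with 1. Hence **8/39 had at least 2 events**. Dividing by n in place of n − 1 leaves the same single solution.

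**3. Physiological arm, ITT alone.** There are 15 affected patients, 38 events, eight patients above 2, and SD 1.6. Full enumeration gives eight solutions: at least 2 events in 8 patients (four solutions), 9 (three) or 10 (one).

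**4. Link to the per-protocol figures.** A mean of 2.4 in 13 patients means 31 events (13 × 2.35 = 30.55; 13 × 2.45 = 31.85). With seven patients above 2 and SD 1.3, two solutions remain: 5, 4, five 3s, one 2, five 1s (SD 1.33), or 4, 4, 4, four 3s, one 2, five 1s (SD 1.26). The two affected ITT patients outside the per-protocol set share 38 − 31 = 7 events, and exactly one of them is above 2, so they split 6+1 or 5+2. The 5+2 split gives an ITT SD of 1.41 or 1.36, which does not match 1.6. The 6+1 split gives 1.60 or 1.55, which does. Both surviving solutions have **9/36 with at least 2 events**.

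The traditional per-protocol figures (13 patients, 21 events, one above 2, SD 0.7) have a solution with the n − 1 SD (0.65: one 3, six 2s, six 1s) and none with the n divisor. This supports reading the SDs as sample SDs.

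**5. RR by cut, ITT.**

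| Cut | Physiological | Traditional | RR (95% CI) | p |
|---|---|---|---|---|
| ≥1 | 15/36 | 15/39 | 1.08 (0.62–1.89) | 0.777 (chi-square) |
| ≥2 | 9/36 | 8/39 | 1.22 (0.53–2.82) | 0.78 (Fisher), 0.64 (chi-square) |
| ≥3 | 8/36 | 2/39 | 4.33 (0.98–19.07) | 0.041 (Fisher) |
| ≥4 | 3 or 4/36 | 1/39 | 3.25 (0.35–29.8) or 4.33 (0.51–37.0) | 0.35 or 0.19 (Fisher) |

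With 8 or 10 in place of 9 at the second cut, RR is 1.08 or 1.35 (Fisher p 1.00 or 0.59). Per protocol, at least 2 events is 8/28 v 7/31: RR 1.26 (0.53 to 3.04), Fisher p = 0.77.

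**6. Whole count, zeros included.** 38/36 = 1.056 and 26/39 = 0.667 events per treated patient, ratio 1.58. On the reconstructed data, a negative binomial model gives a CI of 0.74 to 3.38 (p = 0.23), and a rank test gives p of about 0.52. Neither adjusts for days at risk, which the documents do not give by arm.

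**7. Could the printed cut really mean 2 or more?** No. If only two traditional patients had 2 or more events, they would share 13 events, and the SD would be at least 1.94, not 0.9.

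**The case against.** Several counter-arguments have force.

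- **The excess does not vanish.** At 2 or more events the RR is still above 1, at 4 or more it is 3.25 to 4.33 on very few patients, and total events are 38 v 26. Equal numbers with any event but more patients with three or more is a coherent pattern. A reader might infer from the 1.22 that the schemes are equal on repeated hypoglycemia, or that the arms differ only at the printed cut. The documents support neither; the intervals are too wide to exclude a sizeable excess.
- **It is not the only hypoglycemia-related result below 0.05.** Secondary Results give suspension or change of scheme in 8 v 1 patients (RR 8.67, p = 0.011), and Other Results attribute this to sustained hypoglycemia. That is a separate reported result. However, the suspension rule in Management of Hypoglycemia, "more than 1 event of hypoglycemia after adjustment with a 20% decrease in insulin dose after a first event", can be read as two events in all or as three. On the three-event reading it shares its trigger with the printed cut, so the two results may not be independent support.
- **A reader might infer that the cut was picked after seeing the data.** The documents do not show that. On the three-event reading the cut could come from the protocol's own rule. What can be said is that the statistical section does not name it.
- **The report is not one-sided.** It gives the null at-least-one result first, prints a CI that includes 1 and does not use the word significant for this comparison. Its status follows only from the general p<0.05 rule.
- **The match with the printed p values is limited support.** One surviving distribution returns 0.182 and 0.129 by rank test without continuity correction; the other returns 0.1823 and 0.1296 with it. The match needs a distribution and a test variant chosen together. The count of 9 does not rest on it.

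These points limit the wording. They leave the missing adjacent cut and its size untouched.

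**Conclusion.** The point holds in a limited form and should be fixed. Among the hypoglycemia event comparisons in the Safety Results, the only one with p<0.05 uses a threshold that the statistical section does not name, and the estimate depends heavily on it. Between at least 2 and more than 2 events, the difference moves from 4.5 percentage points (25.0% v 20.5%) to 17.1 (22.2% v 5.1%). Even at the printed cut the ITT evidence is fragile, with a CI that includes 1 beside p = 0.041.

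The traditional count of 8 is determined by the ITT figures. The physiological count of 9 assumes sample SDs and back-solved per-protocol counts of 13/13 and 7/1; without that link it is 8 to 10, and the conclusion is the same. The planned comparison of the hypoglycemia rate is unaffected. The documents support neither a stand-alone four- to eight-fold excess of repeated hypoglycemia nor its absence.

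**What to change.** In Statistical Analysis, specify one analysis of repeated hypoglycemia: the per-patient event count in all treated patients, zeros included, for example a negative binomial model with days at risk as offset. State that counts after scheme suspension may be truncated, mainly in one arm given the 8 v 1 suspensions or changes.

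In Safety Results, tabulate patients with 0, 1, 2 and 3 or more events by arm, with the RR and CI at each cut. The reconstruction is 21/6/1/8 v 24/7/6/2, to be confirmed from the data. Label more than 2 events as an exploratory cut not named in the statistical section. State which reading of the suspension rule was applied, so that the overlap with the 8 v 1 result can be judged.

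The cost is one re-tabulation and one model on existing data, and one p value becomes exploratory. Days at risk per patient must be extracted if they are not already held.
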